### **Statistical Considerations**

Co-investigator [name] (UT Southwestern Division of Biostatistics) is the statistical co-investigator on this project and has assisted in the development of the statistical plan; she will also

Total n=96	Obese	Obese misdiagnosed with asthma	Non- obese
Boys	n=24	n=12	n=12
Girls	n=24	n=12	n=12

direct the data analysis on an on-going basis.

Statistical Plan. Our plan is to complete testing in nonobese and two obese groups, boys and girls separately but concurrently. Thus, sample size calculations are based upon within-gender comparisons per allocation in table at right. In Aims 1-3, comparisons will be made between nonobese, obese, and obese children misdiagnosed with asthma within the same gender with analysis of variance models (ANOVA). Pairwise group comparisons will be made using least squares means contrasts derived from the linear models. Data transformations or nonparametric tests will be utilized as needed to meet analysis assumptions. At baseline, ISSAC and ECRHS asthma screening questionnaire scores will be compared among groups with the Kruskal-Wallis test. Comparisons for Aim 4 will be made similarly, but with the addition of repeated measurements to assess the two obese groups and the nonobese children of the same gender at baseline and at 1 year of follow-up. Additional assessments of gender effects will be performed as part of a secondary analysis, but we are not powering the study to detect interaction by gender. Alpha is set at 0.05 for ANOVA and planned contrast power (PASS 11, NCSS, LLC, Kaysville, UT), described below . Data will be analyzed using SAS version 9.4 (SAS Institute, Inc., Cary, NC).

Aim 1. Our primary variable is FRC measured while seated upright (Aim 1a) and when lying supine (Aim 1b). Based upon our preliminary data for seated FRC (%TLC) in nonobese boys (mean± SD, 42.4±2.5) and obese boys (36.5±6.2), it is calculated that a mean difference in FRC (%TLC) of 5.1 can be detected with statistical power of 81%, alpha=0.05, pooled SD of 5.0, comparing 24 obese to 12 nonobese children or to 12 obese children misdiagnosed with asthma. Our data also show that the differences may be larger for girls than boys, so power for a test between obese girls and obese girls misdiagnosed with asthma will be at least 80%. Similarly, for children lying supine, nonobese boys have an FRC (%TLC) of 34.4±8.8 vs. 23.1±3.4 obese, a more conservative difference of 6.0 %TLC is detectable with 80% power. In our formal protocol, we anticipate being able to make precise and reproducible measurements, and have confidence that we can meet our goals with the sample size proposed. Preliminary data demonstrate that these measures and effect sizes are feasible.

Aim 2. Our primary variable is peak  $\dot{V}O_2$ . From our preliminary peak  $\dot{V}O_2$  (ml/min/kg) for nonobese (41.9±4.9) and obese boys (26.3±3.9), it is calculated that our study will yield power of 80% to detect a clinically relevant mean difference of 4.7 ml/min/kg for obese versus nonobese children or obese children misdiagnosed with asthma, anticipating smaller differences than the 16 ml/min/kg mean difference observed from our data in obese versus nonobese. Effect size estimates for girls are anticipated to be similar.

Aim 3. Our primary variable for Aim 3 is RPB during constant load exercise. Preliminary data from children in our lab show that RPB at constant load is very similar between nonobese and obese children of both genders (e.g., girls, 3.4±0.6 vs. 3.3±1.5), which would not be detectable with a reasonable sample size. This is in contrast with our previous studies of RPB in nonobese (2.1±1.3)  and obese women with DOE (4.7±1.2) , where only 6 subjects would have been necessary per group to detect significant differences. At this time our preliminary sample of children is small, and we anticipate that future experience could be more like that in the adults, but we need to carry out the designed studies at a feasible sample size (96 total including nonobese controls) to find out. These effects contrast with another important variable for Aim 3; the EELV during constant load exercise. Based upon EELV (%TLC) data from obese girls (28±3) during exercise, we would be able to detect differences of 3.2%TLC between the 3 groups at greater than 80% power (also note how low the EELV is in the obese children during exercise). We expect similar differences and power in studies with boys.

**Aim 4.** Primary variables for Aim 4 are change in FRC at rest, peak  $\dot{V}O_2$ , RPB, and EELV during constant load exercise from before to after 1 year of follow-up. We are gaining experience with studies in children; current preliminary data from n=7 obese children yield similar mean differences and standard deviations as in adults. Therefore, based upon the change in EELV during constant load exercise in obese men before ( $35 \pm 5$ ) and after ( $39 \pm 3$ ) a loss of 13% of body fat, and the change in RPB during constant load exercise in obese women before ( $4.7 \pm 1.1$ ) and after ( $3.2 \pm 1.6$ ) weight loss, our sample will have sufficient power (.80,  $\alpha=0.05$ ) to detect meaningful paired differences (e.g., 1.5 in RPB) with weight loss and regular exercise. We will retest all children after ~1 yr. We expect less than 10% attrition and repeated data on nearly all children will be available for this Aim. Combining the two obese groups (with and with asthma misdiagnosis), the children will be divided into obese who lost weight, obese who gained weight, and control normal weight children and respiratory changes will be compared between groups with ANOVA as described for Aims 1-3. While these categorized weight changes have clinical appeal, weight change analyzed as a continuous variable may be more powerful and informative. Hence, change at 1 year minus baseline will also be evaluated with Spearman or Pearson correlations to quantify the association between 1-year weight change and the change for respiratory function, exercise tolerance, and DOE variables and, with the 36 obese participants analyzed (by gender), a correlation of 0.45 can be detected with 80% power.

To evaluate gender effects, baseline and follow-up measurements for FRC, peak  $\dot{V}O_2$ , RPB, and EELV will be analyzed in mixed-effects repeated measures models with the study participant included as a random effect. Interactions between gender, study group (obese, obese misdiagnosed with asthma, nonobese), and time can be assessed as fixed effects; weight change effect will be modeled as a covariate. PAQ-C score changes will also be assessed with repeated measures models.

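### Aim 1 FRC contrasts assume one variance, but the preliminary SDs in boys differ about 2.5-fold; if they hold, the supine nonobese-obese test has 8-17% type I error and 56% valid power at 6.0 %TLC

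*Combined protocol and SAP*

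**What the plan says.** All references are to Statistical Considerations in the combined protocol and SAP.

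- **Model (Statistical Plan).** Nonobese, obese and misdiagnosed children are compared within each sex by ANOVA. "Pairwise group comparisons will be made using least squares means contrasts derived from the linear models". The allocation table gives 12 nonobese, 24 obese and 12 misdiagnosed children per sex. "Alpha is set at 0.05 for ANOVA and planned contrast power".
- **Fallback (Statistical Plan).** "Data transformations or nonparametric tests will be utilized as needed to meet analysis assumptions". No trigger and no unequal-variance method is named.
- **Seated FRC (Aim 1).** Preliminary means and SDs in boys are 42.4 ± 2.5 (nonobese) and 36.5 ± 6.2 (obese). A difference of 5.1 %TLC is given 81% power with a "pooled SD of 5.0, comparing 24 obese to 12 nonobese children or to 12 obese children misdiagnosed with asthma".
- **Supine FRC (Aim 1).** "nonobese boys have an FRC (%TLC) of 34.4±8.8 vs. 23.1±3.4 obese, a more conservative difference of 6.0 %TLC is detectable with 80% power". No SD is stated for this power figure.
- **Size of the preliminary data.** No number of children is given for the FRC SDs. Under Aim 3 the plan says: "At this time our preliminary sample of children is small".

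**The concern.** An ordinary least squares means contrast takes its standard error from one residual variance shared by all three groups. With unequal group sizes, that standard error is too small when a small group has the larger variance, and too large when the big group does. The plan's own SDs show both patterns: supine the 12 nonobese boys have the larger SD (8.8 v 3.4), while seated the 24 obese boys do (6.2 v 2.5).

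If these SDs carry into the study, the two halves of the Aim 1 primary question would be tested at different true error rates, one liberal and one conservative, though both are reported at 5%. The supine power claim would also describe a variance structure unlike the one quoted beside it.

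**Working it through.** **Inputs.** Group sizes 12/24/12; alpha 0.05, taken as two-sided; SDs as quoted. The SD in the misdiagnosed group is not in the documents. I assume it lies between the nonobese and obese values and vary it over that range.

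**1. The plan's figures under a common SD.** For 12 v 24, SE = SD × √(1/12 + 1/24) = 0.3536 × SD.
- Seated: 5.1 / (0.3536 × 5.0) = 2.885. The noncentral t gives 80.0% (df 34, two groups) or 80.6% (df 45, three-group error), against 81% stated. One-sided would give 88%, so two-sided is the right reading.
- Supine: 80% power at 6.0 %TLC needs a common SD of 5.88 (df 34) or 5.93 (df 45). The two-group pooled SD is √[(11 × 8.8² + 23 × 3.4²)/34] = 5.73, which gives about 82%.

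Both stated powers therefore reproduce if the variance is common.

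**2. Standard errors under the quoted SDs, nonobese v obese.**
- Supine, true SE: √(8.8²/12 + 3.4²/24) = √(6.453 + 0.482) = 2.63. With a misdiagnosed SD of 3.4, the ANOVA error SD is √[(11 × 8.8² + 23 × 3.4² + 11 × 3.4²)/45] = 5.26, so the ANOVA SE is 5.26 × 0.3536 = 1.86. That is too small by about 30%.
- Seated, true SE: √(2.5²/12 + 6.2²/24) = 1.46. With a misdiagnosed SD of 6.2, the ANOVA error SD is 5.53 and the SE is 1.95, which is too large.

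**3. True type I error of the nominal 5% ANOVA contrast** (normal simulation, 200,000 replicates, df 45).

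| Contrast | Misdiagnosed SD low | middle | high |
|---|---|---|---|
| Supine (SD 3.4 / 6.1 / 8.8): nonobese-obese | 16.9% | 12.6% | 8.4% |
| Supine: nonobese-misdiagnosed | 12.6% | 13.2% | 14.1% |
| Supine: obese-misdiagnosed | 0.4% | 3.6% | 8.3% |
| Seated (SD 2.5 / 4.35 / 6.2): nonobese-obese | 2.7% | 1.8% | 1.0% |
| Seated: obese-misdiagnosed | 2.7% | 5.0% | 8.1% |

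Welch contrasts stay at about 5% throughout.

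**4. Power with a valid test, nonobese v obese.**
- Supine, Welch df = (6.453 + 0.482)² / (6.453²/11 + 0.482²/23) = 12.7. At 6.0 %TLC the noncentrality is 6.0/2.63 = 2.28 and power is 56%. Power reaches 80% at about 8.0 %TLC and is 98% at 34.4 − 23.1 = 11.3.
- With a misdiagnosed SD of 3.4, the ANOVA contrast does reject about 80% of the time at 6.0, but at a true alpha near 17%.
- Seated, at 5.1 %TLC, ANOVA power is 87%, 84% and 78% for the three misdiagnosed SDs, against 92% with Welch.

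**5. Does the fallback repair it?**
- Supine rank-sum test: about 10% type I error.
- Supine log scale: the SD ratio falls only to (8.8/34.4)/(3.4/23.1) = 1.74. Type I error is 7-12% if the coefficients of variation carry over. It is about 20% if the SDs themselves do and the misdiagnosed SD is 3.4.
- Supine reciprocal: about 6%, but only if SD scales with the mean.
- Seated: transforming makes it worse. The nonobese/obese SD ratio is 0.40 raw, (2.5/42.4)/(6.2/36.5) = 0.35 on the log scale, and (2.5/42.4²)/(6.2/36.5²) = 0.30 as a reciprocal.

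**6. Milder imbalance.** With the misdiagnosed SD equal to the obese SD, type I error is 7.4%, 9.6% and 13.7% at nonobese/obese SD ratios of 1.25, 1.5 and 2.0. At SDs of 6 v 4 it is 6.7-9.7%, and Welch power at 6.0 is 84%.

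**The case against.** The strongest reply is that the SDs may be noise. If they came from 4, 5 or 7 boys per cell (assumed; the plan does not say), the 95% interval for the supine SD ratio is 0.66-10.2, 0.84-8.0 or 1.07-6.2, and the first two include 1. The ratio also changes direction between postures, and no FRC SDs for girls are given. This stands, and it is why every figure here is conditional. It does not support the common-variance choice, however. These are the only FRC SDs in the plan, the design was justified on them, and the test is already liberal at a ratio of 1.25.

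Second, 80% is right for the planned contrast with a common SD, and the implied 5.9 is slightly above the pooled 5.73. That also stands: the figure is no arithmetic error. But it describes a 5% test only if the variances are equal.

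Third, if the preliminary SDs hold, the preliminary difference of 11.3 may hold too, with about 98% power. I accept that the nonobese-obese conclusion would probably survive. The plan nevertheless chose 6.0 as its design difference, and its power claim there is what fails.

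Fourth, the plan promises to adapt when assumptions fail, and a Brown-Forsythe check (the plan names no check) would flag the supine imbalance in about 79-89% of trials. Detection is then likely, but the remedies named do not reliably correct the error rate, and the choice would be made after seeing the data.

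Finally, for supine obese v misdiagnosed no direction of error can be claimed, because the result turns on an SD the documents do not give.

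**Conclusion.** The concern holds, conditional on the quoted SDs in boys. The supine nonobese-obese contrast would run at about 8-17% instead of 5%. The supine nonobese-misdiagnosed contrast would run at about 13-14%, and the seated nonobese-obese contrast at about 1-3%. Valid power for a supine difference of 6.0 %TLC is about 56%, not 80%. These figures assume normal data, full groups of 12/24/12 and a misdiagnosed SD between the nonobese and obese values.

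The power shortfall disappears under a milder imbalance (SDs of 6 v 4), while some type I error inflation remains. This should be fixed, with medium confidence in the size because the preliminary sample is small and its size is not stated. It does not threaten the main nonobese-obese finding if the true difference is near 11.3 %TLC.

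**What to change.** 1. In the Statistical Plan, prespecify group-specific variances for the Aim 1 FRC contrasts instead of leaving the choice to a later judgement. Either use Welch contrasts, or a SAS mixed model with REPEATED / GROUP=group and Satterthwaite or Kenward-Roger degrees of freedom.
2. In the Aim 1 power text, state that 80% supine power at 6.0 %TLC assumes a common SD of about 5.9. Add that under the quoted unequal SDs power is about 56%, with about 8.0 %TLC detectable at 80%.
3. Give the number of children behind each preliminary SD.

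The same method is a reasonable precaution for Aim 4. No size can be put on it there, because no SDs of FRC change are given and the groups are re-formed by weight change.

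**Cost.** A line of code, some SAP wording and a less favourable supine power figure. If the variances are in fact equal, power falls by about 2 points (78.3% v 80.4% at a common SD of 5.9). Under the quoted seated SDs, power for nonobese v obese rises.

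### The group contrasts default to one pooled error although the pilot FRC SDs differ about 2.5-fold; under those SDs the supine obese v nonobese test exceeds 5%, and a test that holds 5% has about 56% power at 6.0 %TLC, not 80%

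*Combined protocol and SAP*

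**What the plan says.** All references are to Statistical Considerations in the combined protocol and SAP.

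- **Method (Statistical Plan).** Within each gender, Aims 1-3 compare obese (n=24), obese misdiagnosed with asthma (n=12) and nonobese (n=12) children by ANOVA. "Pairwise group comparisons will be made using least squares means contrasts derived from the linear models". "Alpha is set at 0.05 for ANOVA and planned contrast power".
- **Fallback (Statistical Plan).** "Data transformations or nonparametric tests will be utilized as needed to meet analysis assumptions". No trigger is given and no unequal-variance method is named.
- **Seated FRC (Aim 1).** The pilot values are for "seated FRC (%TLC) in nonobese boys (mean± SD, 42.4±2.5) and obese boys (36.5±6.2"). The power statement is a difference of "5.1 can be detected with statistical power of 81%, alpha=0.05, pooled SD of 5.0, comparing 24 obese to 12 nonobese children".
- **Supine FRC (Aim 1).** "nonobese boys have an FRC (%TLC) of 34.4±8.8 vs. 23.1±3.4 obese, a more conservative difference of 6.0 %TLC is detectable with 80% power". No supine pooled SD is stated.
- **RPB (Aim 3).** The nonobese v obese pilot example is "e.g., girls, 3.4±0.6 vs. 3.3±1.5".

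No SD is given for the misdiagnosed group.

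**The concern.** A least-squares-means contrast from an ordinary linear model takes its standard error from one residual variance, here on 45 degrees of freedom across all three groups. That is sound if the groups have similar spread. The plan's own figures for its Aim 1 primary variable suggest otherwise, and for supine FRC the larger SD sits in a group half the size of the obese group. In that arrangement the pooled error is dominated by the less variable children, so the standard error for obese v nonobese comes out too small. The same pooled error carries nonobese variability into obese v misdiagnosed, where it does not belong, and makes that contrast too conservative.

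At stake are the 5% level for an Aim 1 primary variable and the meaning of its supine power statement.

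**Working it through.** **Inputs.** Supine SDs 8.8 (nonobese) and 3.4 (obese), seated SDs 2.5 and 6.2, n = 24/12/12, alpha 0.05. Assumed: two-sided tests, normal data, and a misdiagnosed supine SD between 3.4 and 8.8.

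**1. Size of the imbalance.** Supine 8.8/3.4 = 2.59; seated 6.2/2.5 = 2.48, in the opposite direction; RPB in girls 1.5/0.6 = 2.5. Peak VO2 is close to equal: 4.9/3.9 = 1.26.

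**2. The plan's power figures, reproduced.**
- Seated: difference 5.1, SD 5.0, 24 v 12, noncentral t gives 80.0% (34 df) or 80.6% (45 df). The plan says 81%.
- Supine: pooling by the planned sizes, SD = √[(11×8.8² + 23×3.4²)/34] = √(1117.72/34) = 5.73, which gives 82.0% at 6.0. Exactly 80% needs an SD of 5.88 to 5.93. So the stated 80% is consistent with one pooled SD. Equal weighting, √[(8.8² + 3.4²)/2] = 6.67, would give 69.6%.

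**3. Standard error of supine obese − nonobese.**
- True: √(8.8²/12 + 3.4²/24) = √(6.453 + 0.482) = 2.63.
- Pooled over three groups, misdiagnosed SD 3.4: error SD = √[(23×3.4² + 11×3.4² + 11×8.8²)/45] = √(1244.88/45) = 5.26; SE = 5.26 × √(1/24 + 1/12) = 1.86.
- Ratio 1.86/2.63 = 0.71, so the pooled SE is about 29% too small.
- For obese v misdiagnosed the true SE is 3.4 × √(1/24 + 1/12) = 1.20, so the same 1.86 is about 55% too large (1.86/1.20 = 1.55).

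**4. Type I error of the pooled contrast, supine obese v nonobese** (simulation, 400,000 trials per scenario):

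| Misdiagnosed SD | Contrast alone | Only after a significant F test |
|---|---|---|
| 3.4 | 17% | 11% |
| 6.1 | 12.5% | 8.4% |
| 8.8 | 8.4% | 5.5% |

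Welch contrasts give about 5.1% throughout. With a misdiagnosed SD of 3.4, pooled misdiagnosed v nonobese is 12.7% and pooled obese v misdiagnosed is 0.5%.

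**5. Power, supine obese v nonobese.** At 6.0 the pooled contrast rejects about 80% of the time if the misdiagnosed SD is 3.4, and 69% if it is 8.8. For a test that holds 5%, Welch df = 6.935²/(6.453²/11 + 0.482²/23) = 12.7 and noncentrality = 6.0/2.63 = 2.28, giving 56%. Welch power is 80% at 8.0 and 98% at the pilot gap, 34.4 − 23.1 = 11.3.

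**6. Power, supine obese v misdiagnosed (SD 3.4 in both).**

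| True difference, %TLC | Pooled | Welch |
|---|---|---|
| 3.0 | 30% | 66% |
| 3.5 | 44% | 79% |
| 6.0 | 96% | 99.7% |

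**7. Seated FRC (misdiagnosed SD taken as 6.2).** The directions reverse: pooled type I error is 1.0% for obese v nonobese and 8.0% for obese v misdiagnosed. Obese v nonobese power at 5.1 is 78% pooled and 92% Welch.

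**8. The fallback, supine obese v nonobese.** The rank-sum test has a type I error of 9.9%. On the log scale, CVs of 8.8/34.4 = 0.256 and 3.4/23.1 = 0.147 give log SDs of 0.25 and 0.15 (ratio 1.72) and a type I error of 11.8%. For seated FRC the log scale worsens the imbalance: CVs are 6.2/36.5 = 0.170 and 2.5/42.4 = 0.059, a ratio of 2.9 against 2.48 untransformed.

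**The case against.** Several points on the other side have weight.

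- **The SDs are fragile.** Aim 3 calls the preliminary sample of children small, and group sizes for the FRC data are not given. Assuming 5 to 8 children per group, the test of equal variances has a p value of about 0.02 to 0.11. The nonobese SD is the smaller one seated and the larger one supine, which casts doubt on a stable pattern. This stands, and it limits how firmly any size can be stated. It also favours a method that is valid whether or not the variances are equal. With milder supine SDs of 4 and 6.5, the pooled type I error is still about 11%.
- **17% is one corner of the range.** It needs a misdiagnosed SD of 3.4 and contrasts not gated by the F test. The plan settles neither. This stands; the range in step 4 is the fair statement.
- **The imbalance is not general.** At the peak VO2 SDs the pooled type I error is about 7.5%, or 4.1% if gated (misdiagnosed SD taken as equal to obese), and the adult RPB SDs quoted under Aim 3 (1.3 and 1.2) are nearly equal. This stands; the point is mainly about FRC.
- **The plan already provides for failed assumptions.** It does, and contrasts from linear models could be fitted with separate variances. But the clause names no such method, and what it does name leaves about 10% to 12%.
- **The main supine comparison is safe at the pilot gap.** This stands: power there is about 98% even with Welch.

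**Conclusion.** The point holds as a should-fix. By default the planned contrasts use one pooled error, which the plan's own FRC SDs do not support. If the printed supine SDs hold, obese v nonobese is tested at a true level of about 8% to 17%, or about 5.5% to 11% with F-test gating. The 80% at 6.0 %TLC is then reached only by a test that exceeds 5%; a valid test has about 56%. These sizes rest on normal data, small-pilot SDs of unknown precision, and an assumed misdiagnosed SD.

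Two stronger readings are not supported. A reader might infer that the obese v misdiagnosed contrast generally loses about half its power. That is true only near 3.0 to 3.5 %TLC, which the plan does not name as a target; at its 6.0 the figures are 96% and 99.7%. A reader might also infer that 80% at 6.0 is simply not attained. The pooled test does reject about 80% of the time for obese v nonobese if the misdiagnosed SD is 3.4, and obese v misdiagnosed exceeds 80% under the same assumption. The shortfall belongs to obese v nonobese with a test that keeps its level.

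**What to change.** - **Statistical Plan.** For Aims 1-3, make the primary method a group model with a separate residual variance per group (SAS PROC MIXED, REPEATED / GROUP=, with Satterthwaite or Kenward-Roger degrees of freedom), or Welch ANOVA with Welch contrasts. Pre-specify it rather than leaving it to be invoked as needed.
- **Aim 1 power paragraph.** Restate supine obese v nonobese power as about 56% at 6.0 %TLC, or 80% at about 8.0 %TLC, under the printed SDs. Say that these SDs come from a small pilot.

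**Cost.** A line of SAS code and some SAP wording, with no change to recruitment or sample size. The supine power figure becomes less favourable. If the variances prove equal, about 2 points of power are lost: at the plan's seated 5.1 with SD 5.0, 80.6% pooled against 78.6% Welch.

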**Expected results.** We *expect* that altered respiratory function and breathing mechanics will be both prevalent and significant in obese children, primarily a reduced FRC, which may be correlated with other obesity-related changes in body composition. Furthermore, we expect that obese children with respiratory symptoms misdiagnosed as asthma will have greater changes in obesity-related respiratory function and/or differences in peripheral airways function making them more susceptible to low lung volume breathing. We also *expect* to have a better understanding of the magnitude, mechanism, and importance of the respiratory effects in obese children and the differences (if any) between obese boys and girls.

Interpretation of results. We will interpret these results to suggest that obese children have significant obesity-related alterations in respiratory function, which predispose them to potentially clinical breathing limitations especially in obese children misdiagnosed with asthma, all through a common mechanism of low lung volume breathing. This is important knowledge for the healthcare provider who may assume obese children have mostly normal lung function and that any respiratory symptom in obese children is primarily related to asthma.

**Aim 1b.** Introduction: at Rest Lying Supine. The *working hypothesis* is that childhood obesity will alter respiratory function and breathing mechanics when lying supine. Also, we propose that obese children with respiratory symptoms misdiagnosed as asthma will have greater changes in lung volumes when supine and/or differences in peripheral airways function making them more susceptible to low lung volume breathing. The *rationale* behind the proposed research centers on the fact that excess fat on the chest wall will push FRC to extremely low levels in the obese children especially when lying supine, thus creating the potential for significant breathing limitations especially in obese children misdiagnosed with asthma. To further test the hypothesis, we will add an external weight (2.5kg) between the xiphoid process and umbilicus of supine nonobese children and measure the change in FRC. This weight is lower than the 5kg that we used in preliminary testing, and is representative of the difference in chest wall fat observed between our obese and nonobese children.

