Methodology, experimental protocol and measurements. The strategy will be to measure respiratory function and breathing mechanics when lying supine at the cardiopulmonary exercise station. Baseline data will consist of 15 min of sitting upright in a chair. After obtaining a steady-state, we will measure HR, SpO2% (by pulse oximetry), PETCO2, ratings of perceived breathlessness (RPB; Borg 0-10 scale), respiratory function (FVC&IC by spirometry, FRC by helium dilution, & calculate TLC=IC+FRC) including breathing pattern and tidal flow-volume loops. Measurements will be made in duplicate, and averaged for analysis, which has worked well in preliminary studies in children. During 15 min of lying supine, we will measure the same variables in the same way as above. In nonobese children only, we will add a 2.5kg external weight between the xiphoid process and umbilicus to simulate the effects of abdominal fat on FRC and make the same measurements.

Expected results. We expect that in comparison with nonobese children many obese children will have a marked reduction in FRC when lying supine, which may be correlated with other obesity-related measures of body composition. Furthermore, we expect that obese children with respiratory symptoms misdiagnosed as asthma will have greater changes in obesity-related respiratory function when lying supine. We anticipate a decrease in FRC with the external abdominal weight in the nonobese children. We expect this change will be *qualitatively* similar to that observed in obese children. We also *expect* to have a better understanding of the importance of changes in supine respiratory function in obese children, and the differences (if any) between obese boys and girls.

Interpretation of results. We will interpret these results to suggest that obese children have significant obesity-related alterations in respiratory function when lying supine, which predispose them to potentially clinical breathing limitations, especially in obese children misdiagnosed with asthma, all through a common mechanism of low lung volume breathing. This is important knowledge for the healthcare provider who sees obese children with symptoms of orthopnea or sleep related complaints. These findings would stress the need for further clinical/physiological testing in obese children with symptoms when lying supine (i.e., more testing than simple seated spirometry).

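### Aim 1b compares supine FRC level between groups, which shows whether FRC is low when supine but not whether lying down adds to the seated deficit; the paired seated and supine data go unused

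*Combined protocol and SAP*

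**What the plan says.** **Endpoint.** Statistical Considerations, Aim 1: "Our primary variable is FRC measured while seated upright (Aim 1a) and when lying supine (Aim 1b"). These are two levels; no change between postures is named.

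**Analysis.** The Statistical Plan says that for Aims 1–3 "comparisons will be made between nonobese, obese, and obese children misdiagnosed with asthma within the same gender with analysis of variance models (ANOVA"). Repeated measures enter only later: "Comparisons for Aim 4 will be made similarly, but with the addition of repeated measurements", and there the repetition is baseline and one year. The mixed model described under Aim 4 has gender, study group and time as fixed effects, with weight change as a covariate and no posture term.

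**Sizing.** Seated: "a mean difference in FRC (%TLC) of 5.1 can be detected with statistical power of 81%, alpha=0.05, pooled SD of 5.0", for 24 versus 12 children within gender. Supine: "a more conservative difference of 6.0 %TLC is detectable with 80% power"; no planning SD is given for this figure.

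**What Aim 1b wants to say.** Its working hypothesis is that obesity alters respiratory function in the supine position. Its rationale goes further: chest wall fat is held to drive FRC very low in particular when the child lies down. It also proposes that "obese children with respiratory symptoms misdiagnosed as asthma will have greater changes in lung volumes when supine". The interpretation is addressed to providers who see orthopnea or sleep complaints, and says that children with supine symptoms need "more testing than simple seated spirometry".

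**What is measured.** The Aim 1b session takes a seated baseline, including FRC by helium dilution in duplicate, and then repeats the same measurements supine.

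**The concern.** A group difference in supine FRC has two possible sources: the deficit already present when seated, and any extra fall on lying down. A comparison of supine levels adds them together. The planned test can therefore be positive when obese and nonobese children lose exactly the same FRC on lying down.

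The supine-specific part of the message needs the second source. If Aim 1b is positive only because the seated deficit carries over, a statement that the supine position worsens the deficit, or that supine testing adds to seated FRC testing, would rest on a result that says nothing about posture. Reading the seated and supine ANOVAs side by side does not repair this, because two separate tests, whether both significant or only one, are not a test of the difference between postures.

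**Working it through.** **Inputs** (Statistical Considerations, Aim 1; boys only; preliminary group sizes not given)
- Seated FRC, %TLC, nonobese boys first: "42.4±2.5) and obese boys (36.5±6.2". Gap 42.4 − 36.5 = 5.9.
- Supine FRC, %TLC: nonobese 34.4±8.8, obese 23.1±3.4. Gap 34.4 − 23.1 = 11.3.
- Allocation 24 versus 12 within gender. Alpha 0.05, taken as two-sided because the plan does not say.
- Seated–supine correlation r: not given, so a range is assumed.

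**Formula.** Two-sample t-test, noncentrality = difference / (SD × √(1/24 + 1/12)) = difference / (SD × 0.3536), 34 degrees of freedom.

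**Step 1: the plan's own figures**
- Seated: 5.1 / (5.0 × 0.3536) = 2.885, power 80.0% (80.6% with the three-group error df of 45), against 81% stated. Reproduced.
- Supine: pooling the preliminary SDs at 24 and 12 gives √[(23 × 3.4² + 11 × 8.8²)/34] = 5.73, and power for 6.0 is 82%. Exactly 80% implies SD 5.88. The unweighted root-mean-square SD, √[(3.4² + 8.8²)/2] = 6.67, gives 70%. The stated figure is therefore consistent with an allocation-weighted SD of about 5.7–5.9.

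**Step 2: the planned supine test if posture adds nothing.** Set the supine gap equal to the seated gap, 5.9.
- SD 5.88: 5.9 / (5.88 × 0.3536) = 2.84, power 79%.
- SD 5.73: 2.91, power 81%.
- SD 6.67: 2.50, power 68%.

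A simulation of this case (common SDs 5.0 seated and 5.88 supine; r = 0.3, 0.5, 0.8; 20,000 runs each) gave 78–79% rejections for the level test and 4.9% for a test of the within-child change. At the observed supine gap of 11.3 the level test has over 99% power. It is thus likely to be positive with or without an added postural effect.

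**Step 3: a contrast that isolates posture.** Falls between group means are 42.4 − 34.4 = 8.0 (nonobese) and 36.5 − 23.1 = 13.4 (obese), a difference of 5.4 %TLC. The SD of the change in each group is √(s₁² + s₂² − 2r·s₁·s₂), with s₁ the seated and s₂ the supine SD. At r = 0.5:
- obese √(6.2² + 3.4² − 6.2 × 3.4) = 5.38
- nonobese √(2.5² + 8.8² − 2.5 × 8.8) = 7.85
- pooled √[(23 × 5.38² + 11 × 7.85²)/34] = 6.29
- noncentrality 5.4 / (6.29 × 0.3536) = 2.43, power 66%

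| Assumed r | Pooled SD of change | Power for 5.4 %TLC | Detectable at 80% | Power, Welch test | Power, common SDs 5.0 and 5.88 |
|---|---|---|---|---|---|
| 0.3 | 6.93 | 57% | 7.07 | 46% | 63% |
| 0.5 | 6.29 | 66% | 6.41 | 52% | 77% |
| 0.7 | 5.57 | 76% | 5.67 | 60% | 93% |
| 0.8 | 5.17 | 82% | 5.27 | 64% | 99% |

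With the preliminary SDs and a pooled test, 80% power needs r of roughly 0.8.

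**The case against.** The strongest defence is that the endpoint matches the hypothesis as written. Aim 1b hypothesises altered function when supine and expects lower supine FRC than in nonobese children, and the proposed mechanism is breathing at a low absolute lung volume. A comparison of supine levels tests that. This stands, and it is why the level should remain primary. A reader might infer that Aim 1b has the wrong primary endpoint and that a change score should replace it. The documents do not support that, and the power in the working shows that replacement could cost a good deal.

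Other tempting readings also go too far:
- The phrase about greater changes when supine might be taken as an explicit hypothesis about seated-to-supine change. The protocol uses the same phrase in Aim 1a, where all measurements are seated, and in Aim 3, during cycling. It may simply mean larger alterations.
- The seated gap of 5.9 and the supine figure of 6.0 look like a match. One is an observed gap and the other a detectable difference, so their closeness proves nothing. The calculation in step 2 does not depend on it.
- The closing message refers to spirometry, which does not give FRC, so it can be read narrowly. But Aim 1a already measures seated lung volumes by plethysmography, so a claim that supine testing adds to seated FRC testing would still need its own evidence.
- The preliminary supine gap (11.3) is nearly twice the seated gap (5.9), which may suggest that the postural effect is already shown. These are differences of group means. The plan does not say that the same boys supplied both values or that one method was used.

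None of this supplies a planned analysis of posture.

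**Conclusion.** The point holds in a limited form. The Aim 1b primary comparison is valid for its narrow hypothesis, and the 6.0 %TLC figure is not an arithmetic error. What is missing is any planned analysis that separates an added supine effect from a carried-over seated deficit. With a carried-over gap of 5.9 %TLC the planned test would be positive about 79–81% of the time (SD 5.88–5.73), or about 68% at SD 6.67.

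This rests on a two-sided 0.05 test, 24 versus 12 children, and preliminary values from boys in samples of unstated size. It applies to obese versus nonobese children. No preliminary FRC is given for the children misdiagnosed with asthma, so no carry-over can be sized for them, although the same gap in the analysis plan applies. The power of the added contrast depends on a correlation that the documents do not report.

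**What to change.** 1. Keep supine FRC level as the Aim 1b primary variable, and state the SD behind the 6.0 %TLC figure.
2. Prespecify as key secondary the between-group difference in within-child supine-minus-seated FRC, or equivalently a group-by-posture term, using the paired helium-dilution measurements from the Aim 1b session and not the Aim 1a plethysmography values. Say how the change is expressed: TLC is calculated as IC plus FRC in each posture, so a change in %TLC also reflects any shift in the denominator.
3. Allow a conclusion that the supine position worsens the deficit, or that supine testing adds to seated FRC testing, only if this contrast supports it.
4. State its detectable difference over a range of correlations. With the preliminary SDs this is 7.07, 6.41, 5.67 and 5.27 %TLC at r = 0.3, 0.5, 0.7 and 0.8. Say whether the test assumes equal variances, since the preliminary SDs differ widely between groups.

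No new measurement is needed. The cost is one extra contrast, which may have less than 80% power within gender, so a nonsignificant result should not be read as showing no postural effect.
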